## 5. Study Design

### 5.1. Describe the study design type.

This is a case-control study recruiting 19,500 bipolar disorder cases and 15,000 controls in people of Asian descent. Genetic analysis will be performed to identify genetic variants associated with BP-I and explore phenotypic variance in BP-I and its relationship with genetic signatures and environmental risk factors. If funded, new study recruitment will take place in five countries in Asia, which covers 40% of the Asian population. Sites were selected on the basis of the following criteria: 1) proven track record of psychiatric research; 2) availability of research personnel and the necessary research infrastructure to be able to recruit thousands of participants; 3) existing trusted relationships from prior collaborations. Each of the countries where participants will be recruited from has enormous geographic and genetic diversity within and between them (1-3), which is likely to improve the ability of this research to answer the study objectives.

### 5.2. Does the study involve more than one participant group?

No  Yes: *If yes, identify each group here and throughout all applicable sections.*

Yes, the participant groups involve cases and controls.

### 5.3. Indicate the total duration of a participant's involvement.

The total study visit will be around 3 hours in total. It includes:

- Consenting: 30 minutes
- Questionnaires and assessments: 90-120 minutes
- Blood draw: 10 minutes

### 5.4. Indicate the total number of participants to be screened (if applicable) and/or enrolled (i.e., signed consent form). If the proposed research involves secondary data analyses only, indicate the number of data, documents, records, and/or specimens that will be obtained.

The four-year target enrollment of prospective collections across all of the sites is ~34,500. We expect to recruit an estimated 19,500 cases and 15,000 controls. This amounts to an average annual enrollment of more than 4,475 cases per year and almost 3,425 controls per year across all five countries. Below is a table indicating the planned recruitment numbers by each participating site:

## Recruitment Milestones

| Site         | Type of Subject (Cases vs. Controls) | End of Y1 (cumulative) 9/1/22 - 8/31/23 | End of Y2 (cumulative) 9/1/23 - 8/31/24 | End of Y3 (cumulative) 9/1/24 - 8/31/25 | End of Y4 (cumulative) 9/1/25 - 8/31/26 | Total |
|--------------|--------------------------------------|---|---|---|---|-------|
| Japan        | Cases                                | 350                                     | 950                                     | 1550                                    | 2000                                    | 3000  |
|              | Controls                             | 200                                     | 500                                     | 800                                     | 1000                                    |       |
| India        | Cases                                | 2000                                    | 5000                                    | 8000                                    | 10000                                   | 20000 |
|              | Controls                             | 2000                                    | 5000                                    | 8000                                    | 10000                                   |       |
| Korea        | Cases                                | 600                                     | 2000                                    | 3400                                    | 4000                                    | 6000  |
|              | Controls                             | 400                                     | 1000                                    | 1600                                    | 2000                                    |       |
| Singapore    | Cases                                | 100                                     | 250                                     | 400                                     | 500                                     | 1000  |
|              | Controls                             | 100                                     | 250                                     | 400                                     | 500                                     |       |
| Taiwan       | Cases                                | 500                                     | 1500                                    | 2500                                    | 3000                                    | 4500  |
|              | Controls                             | 250                                     | 750                                     | 1250                                    | 1500                                    |       |
| Total | Cases                         | 3550                                    | 9700                                    | 15850                                   | 19500                                   | 34500 |
|              | Controls                      | 2950                                    | 7500                                    | 12050                                   | 15000                                   |       |

**5.5. List inclusion and exclusion criteria, including age ranges of all participants, and describe the screening process. Provide a rationale for any specific exclusion criteria.**

All the sites from five countries use the same recruitment protocol to ensure study consistency. Potential cases will be recruited from outpatient and inpatient clinics with the following inclusion criteria:

1. Any subjects who meet DSM-5 the diagnostic criteria for Bipolar I Disorder;
2. Age at recruitment is 18-75 years old
3. Age of the first episode (either major depressive episode or manic episode) prior to age 50;
4. At least three years since the initial diagnosis of Bipolar Disorder.

Cases will be excluded if:

1. Persons who are currently involuntarily detained
2. Persons who are currently acutely psychiatrically illness
3. Anyone whose treating physician believes that participation could be harmful to them
4. Any history of a psychiatric illness caused by a neurologic condition (including mental disorders caused by epilepsy, cerebral tumor, CNS infections, or head trauma)

5. Any history of moderate or severe intellectual disability
6. Any history of a diagnosis of a mental disorder secondary drug or alcohol use

Selected controls will be recruited at each site and matched on ascertainment location, ethnicity, age at ascertainment and sex. Controls will be recruited following the inclusion criteria below:

1. Any subjects who screens negative for bipolar disorder I or II, schizoaffective disorder and schizophrenia
2. Age at recruitment is 18-75 years old

Exclusion criteria of controls are:

1. Any history of mania or psychosis or diagnosis of any DSM-5 bipolar diagnosis or psychotic disorder
2. Any history of a psychiatric illness caused by a neurologic condition (including mental disorders caused by epilepsy, cerebral tumor, CNS infections, or head trauma)
3. Any history of moderate or severe intellectual disability
4. Any history of a diagnosis of a mental disorder secondary to drug or alcohol use.

Note that a diagnosis of major depressive disorder (without psychosis) or a diagnosis of a substance use disorder itself will not be exclusion criteria for controls in order to avoid biases in our genetic findings with signals related to these relatively common conditions.

**Rationales for exclusion criteria in cases:**

1. We excluded the patients who are involuntarily detained in the hospital to make sure there's no coercion in participating the study
2. For the safety and wellness of patients, those who are under acute illness will be excluded from the study
3. Premorbid mental disorders and previous history of drug use are excluded to eliminate the confounding factors in the analysis.

**5.6. Describe study procedures.**

Participants will 1) undergo an interview with research assistants about basic demographic information, including information on putative environmental risk factors for bipolar disorder, and subject reports on past psychiatric diagnoses as well as history of affective and psychotic disorders in first degree relatives. 2) provide a small blood specimen (under 50 milliliters).

During the screening, research assistant will review medical charts / ask participants the year and month of the initial diagnosis to confirm the eligibility. Another study staff will double

[figure not shown]
check the participant’s eligibility to make sure all the criteria are met before enrolling to the study.

Additionally, cases will be interviewed by a clinician: 1) The mood and psychotic disorder modules from the Structured Clinical Interview for DSM 5 (SCID-5) will be administered to confirm that cases meet inclusion criteria and to collect item-level information about specific symptoms and course of illness and, 2) a custom brief instrument (the Bipolar Phenotype Inventory), in order to collect data on domains of functioning, psychopathology and other history. Items on this instrument will be specifically chosen to capture variation where there is existing evidence that such variation tracks with genetic heterogeneity. This instrument will be administered through patient interview, and, where available, informant interview and/or review of records.

The phenotyping battery is the whole questionnaire that will be administered by local researchers, including SCID and demographic information.

As stated, screening questionnaires, interviews, and blood tubes will be identified only with a subject ID number. The coding key and consent forms, plus any re-contact information, must and will be maintained in a coded spreadsheet in a secure location at each local site. Only authorized and trained research staff will have access to these files.

In addition, due to COVID-19 outbreak, all the participants coming to the clinic will be required to wear surgical masks. There will also be free masks at the front desk for participants to wear. Participants will be asked to take temperature, report if they have cough, shortness of breath, or other flu symptoms, travel and contact history. All the research staff will wear PPE when conducting those study procedures.

**5.7. Does the study involve the use of deception and/or incomplete disclosure?**

**No**  **Yes:** *If yes, explain the use of deception/incomplete disclosure and describe why it is necessary to achieve the goals of the study.*

**5.8. When all research-related study procedures are complete, are there plans for long-term follow up?**

**No**  **Yes:** *If yes, indicate what data will be collected during this period*

The study doesn't have plans for long-term follow up. If the study have unique genetic findings, we may ask certain participants with or without those genetic variants if they are willing to participate in another study in future. The option to be contacted in the future study is indicated in the informed consent.

**5.9. Does the study involve the collection of specimens (e.g. blood, cells, tissues, fluids, secretions, recombinant or synthetic nucleic acids, biological toxins, bacteria, virus, fungi, etc.)**

No  Yes: *If yes, indicate the [COMS Registration Number](#) or plans to obtain COMS approval.*

The study will collect blood samples from participants.

**5.10. Does the study involve the use of existing data, documents, records, and/or specimens for secondary analysis?**

No  Yes: *If yes, indicate how, when, where, and from whom data, documents, records,*

*The study involves review of medical records during screening and data collection process. The medical records will only be available at local research sites and will only be reviewed by researchers who have access.*

**5.11. Are there provisions for medical and/or psychological support resources available to participants (e.g., in the event of incidental findings, research-related stress)?**

No  Yes: *If yes, describe the provisions and their availability.*

The findings from the systematic psychiatric evaluation may indicate information on accurate psychiatric diagnosis, presence or absence of psychiatric symptoms, and longitudinal course of psychiatric disorder, which will be provided to participants to manage overall psychiatric illness. Also, we will notify participants if their data assessed through the participation has a significant impact on health or requires immediate action for psychiatric treatment.

During the study process, if a participant feels stress or uncomfortable, the participant may take a break or skip the session. The study team will provide psychological support for the research-related stress. If a subject indicates potential harm to themselves or others, the study team will refer the subject to the specialist for consultation.

We do not currently plan to release results of genotyping analyses, including any incidental findings, to subjects, their families, or to third parties. This has also been our policy on previous genetic studies of similar disorders. The reason for this policy is that we do not believe that these results will have a straightforward or predictive interpretation, at an individual level, in the foreseeable future. We would only modify this policy in accordance with IRB standards, if at some point we are able to provide accurate and quantifiable risks to individuals for the disorders that we are studying. Because the clinical relevance of the data to be acquired is yet to be determined, no other individual information will be shared with study participants.

**5.12. Describe the data and safety monitoring plan for the study. This plan should outline how study progress will be monitored throughout the lifecycle of the research to ensure the safety of subjects, as well as the integrity and confidentiality of data.**

**Monitoring Plan**

The study will be overseen by Broad PI [name]. Under [name] supervision, the Broad project manager will routinely communicate and monitor the study progress:

1. Once the study is approved by both IRB, we will invite researchers from each site to Broad for initiation training (we may switch to virtual training due to pandemic). The training will cover:
  - a. Screening and assessing participants with study tools and questionnaires
  - b. Obtaining and documenting informed consent
  - c. Use of logs, including enrollment log, staff delegation log and training log
  - d. Adverse events report and Notes to File
  - e. Collecting data with REDCap (REDCap is a password protected data collection tool)
  
2. The project manager will hold virtual conference with each site every 2 weeks, checking in on compliance and data collection:
  - a. Study enrollment log will be reviewed bi-weekly for monitoring enrollment and compliance
  - b. REDCap data forms will be reviewed for any missing data or queries
  - c. New research staff and any unexpected events will be reported and discussed during the meeting
  
3. PI and the project manager will go site visits every year, monitoring the study and providing refresher training.
  - a. The Broad project manager will randomly select 10% enrollment documents for review, including informed consents, enrollment logs, Notes to Files, and other documentation.
  - b. Regulatory documents including local IRB approval, site training logs, delegation logs will also be reviewed on sites.
  - c. Data confidentiality will be monitored during the site visits to make sure sites have secured places to store participants' documents.

### **Data Safety Plan**

Throughout the study, confidentiality of participants will be the first priority. Plans to maintain confidentiality include the following:

1. All study staff across all sites will be trained, with ongoing supervision, to make confidentiality the first priority. All staff needing to access confidential health information or needing to interact with participants will complete Protection of Human Research training before being given authorization to do so.
2. All interviews will be conducted privately. If informant interviews are conducted, information received from individual family members will not be shared with any other family member.

3. All identifying information will be kept in locked areas and will not be shared with other investigators.
4. Consent forms and re-contact information, if given, will be stored in locked cabinets separate from demographic and diagnostic data.
5. The most serious risk would be identification of individuals in the publicly shared database. To prevent this, computerized data files provided to other investigators will not include names, addresses, date of birth, physical descriptions, or other individual-specific information. Only numerical ratings, clinical information, and final diagnoses will be provided. Published material will not identify subjects.
6. Some authorities on genetic studies have expressed concerns that it might someday become possible to identify subjects by comparing DNA test information from research with DNA information that might someday be found in medical records. This information could conceivably be used to deny insurance or employment to persons at risk for specific diseases. At present, there are no DNA marker data in routine medical records that could be used to identify subjects, and DNA information from research is not publicly available.

**5.13. Are there any anticipated circumstances under which participants will be withdrawn from the research without their consent?**

**No**  **Yes:** *If yes, describe the circumstances for withdrawal as well any associated procedures to ensure orderly termination, appropriate referrals, and/or follow-up care.*

**6. Recruitment Methods**  **N/A.** *Skip to next section.*

*Upload recruitment materials to the “Local-Site Documents” page in ESTR.*

**6.1. Indicate how, when, where, and by whom participants will be recruited.**

**Provide a list of materials used to recruit participants, e.g., emails, posters, and/or scripts here.**

Please note that sites recruitment materials are being reviewed by local IRB, we will submit the approved materials via an amendment. Neither consents nor recruitment materials will be implemented until both Harvard and the local IRB have approved.

Please note that only Singapore, Taiwan and Korea will start enrollment in this approval. Study details in Japan and India will be submitted in a modification when grant is awarded.

**Singapore Recruitment**

The Institute of Mental Health of Singapore will recruit 1000 participants (500 cases, 500 controls). All participants are over 21 years old (In Singapore below 21 years old is minor).

As Singapore is a multi-ethnic country, the study population will consist of Chinese and South Asians. Research team is well trained who understands best about local culture, religion of different ethnic groups and social delicacies. Recruitment flyers containing brief information about the study, inclusion/exclusion criteria and study contact information are presented to participants in local languages, including English, Chinese and Tamil. Recruitment conversations are done in the potential participant's preferred language by a bachelor's level Research Assistant.

Ascertainment and Screening of Cases:

Patients are recruited from both inpatient and outpatient services. For inpatient recruitment, only patients from open wards and are in a stable status will be enrolled to the study. In outpatient clinics, study flyers are handed to patients in the waiting room. Clinicians will explain the study and then refer patients who are interested in the study to the research team. Research team will describe the study in local language, give participants informed consent to read and answer all the questions they may have. Consenting process involving the collection of blood samples, structured clinical interviews and assessments, allowing access to information contained in their medical record, and broad consent to allow sharing of coded samples/data with other researchers.

Inclusion and exclusion criteria for cases: consistent with the study criteria.

Ascertainment and Screening of Controls:

We will recruit 500 controls, matched to the cases on age, gender, race and educational level attained and geographical location by advertising widely through study flyers in communities. Controls will also be recruited from other research databases with controls willingness to be recontacted for other studies. Those interested in participating will be directed to study staff located on-site, or will contact study staff by phone or email. Study staff will describe the study and perform a brief eligibility screening questionnaire. Individuals passing this initial screen will be invited to enroll, either while at the clinic during their routine visit, or during another scheduled time. The informed consent process for control participants will involve consenting to blood sampling, screening assessment, and broad consent for sharing. Participants will be compensated for transportation costs.

Inclusion and exclusion criteria for controls: consistent with the study criteria.

**Taiwan Recruitment**

All recruitment conversations are done in the potential participant's preferred language by a research assistant or study nurse, either in Mandarin Chinese or Taiwanese language. We enroll Taiwanese Han Chinese with both genders in this study. We plan to recruit 3000 cases and 1500 controls in total over four years. Because Taiwan legal adult age is set at 20 y.o., therefore, only adult men and women between 20 and 70 will be recruited within this study. Recruitment materials include flyers and posters of both hard copy format and electronic file format for social media recruitment. Flyers are present in Mandarin Chinese and containing

brief information about the study, inclusion/exclusion criteria are shown in the following section. Contact and more detailed information will be explained to patients by research assistants or psychiatrists. The target number of participants was carefully calculated based on estimated caseloads of patients with the diagnoses of interest in each of the study sites following several discussions with clinicians who practice at the study sites. We estimate approximately 50% participation rate, because participation is relatively slight-impact. In addition, we will re-contact patients (500~) and controls (500~) who participated in previous studies to invite them to join the proposed project. Those who agree to participate will re-sign the informed consent.

Cases – Patients with bipolar I disorder, or schizoaffective disorder-mania type are recruited primarily from clinical settings from both inpatient and outpatient facilities in central and regional hospitals. Patients will be recruited in the Northern, Central, Southern, and East-coast cities. In out-patient departments, psychiatrists briefly introduce the study to eligible patients, if patients are willing to join the study, then 1) referral to the research assistants to introduce the details of the study and sign the informed consents. 2) leave the contact information, the research assistants will contact them within seven days. For psychiatric inpatients, patients will be referred to a study assistant by psychiatrists when their mood is relatively stable. The study assistant introduces the details of the study and signs an informed consent in the ward, the detailed interview will be after the day of discharge. Cases are recruited predominantly on clinics and wards from a network of university hospitals in the four main regions in Taiwan.

Inclusion and exclusion criteria for cases: consistent with the study criteria and we will additionally exclude cases with substance induced bipolar disorder, mental retardation, schizophrenia, dementia, and HIV infection. Aboriginal in Taiwan will be excluded since our main target population is Han Chinese.

Controls - We ascertain controls from persons who present for treatment of general medical conditions at general medical hospitals that draw from similar catchment areas to the psychiatric facilities, as well as community controls. Controls must screen free from any psychiatric disorders history. We also use flyers of both hard copy format and electronic file format for social media recruitment. Willingness participants from social media actively contact and leave the message to the study team, study assistants will contact them to introduce the details of study and sign the informed consent and interview questionnaires. The local study team is the first point of contact for the patient and will explain the study and enroll controls into the study.

Inclusion and exclusion criteria for controls: consistent with the study criteria. Aboriginal in Taiwan will be excluded since our main target are Han Chinese

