### 2.2 Describe the significance of the research, and how it will contribute to generalizable knowledge.

**A-BIG-NET will generate a BP-I genetic resource of 27,500 cases and 16,000 controls with rich phenotypic information and genetics data from a novel technology combining low-pass whole genome (1xWGS) and deep exome sequencing (55xWES).** We will focus on BP-I disorder to maximize genetic homogeneity. This resource is powered to discover new genetic associations with BP-I across the allelic spectrum in the Asia populations, and will reveal, for the first time, the comparative genetic architecture of BP-I across major world populations. Combining schizophrenia (SCZ) genetics resources that our team has already put together (15,000 cases and 14,000 controls), we will further expand the scope of psychiatric genetics by extending to two of the most important and severe adult psychiatric disorders in Asian populations.

This proposed study will dramatically increase the diversity of genetic discovery efforts by creating a BP-I genetics resource with rich phenotyping data, an important step towards reducing health disparities and accelerate gene discovery for psychiatric disorders in cohorts of diverse ancestry to advance global mental health discovery and equity.

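### Taiwan's recruitment text names schizoaffective disorder as a case diagnosis, contrary to the study-wide BP-I-only criterion, and the number of cases affected is not stated

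*Protocol*

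**What the plan says.** Section 5.5 of the protocol sets the case criterion: "Any subjects who meet DSM-5 the diagnostic criteria for Bipolar I Disorder". It introduces the criteria with the statement "All the sites from five countries use the same recruitment protocol to ensure study consistency". Section 2.2 gives the reason for the restriction: "We will focus on BP-I disorder to maximize genetic homogeneity".

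The Taiwan part of section 6.1 defines its cases differently: "Patients with bipolar I disorder, or schizoaffective disorder-mania type are recruited primarily from clinical settings". A little further on it describes its case criteria as "consistent with the study criteria and we will additionally exclude cases with substance induced bipolar disorder, mental retardation, schizophrenia, dementia, and HIV infection". That list of extra exclusions includes schizophrenia but not schizoaffective disorder. Taiwan's size is given in the same place: "We plan to recruit 3000 cases and 1500 controls in total over four years".

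Section 5.6 says that the SCID-5 mood and psychotic disorder modules "will be administered to confirm that cases meet inclusion criteria and to collect item-level information".

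The Korean text names bipolar I patients only, and the Singapore text refers back to the study criteria. Details for Japan and India are deferred to a later modification.

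**The concern.** In a case-control study, the case definition determines what every association estimate means. Here one of the first three countries cleared to enrol (section 6.1 lists Singapore, Taiwan and Korea) states a wider definition than the study does.

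Schizoaffective disorder is not a loose synonym for BP-I in this protocol. The control criteria in section 5.5 list it separately from bipolar I or II and from schizophrenia.

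Aim 3c is the most exposed, because it analyses BP-I and schizophrenia samples of Asian ancestry jointly to separate their genetic architecture. Patients with a schizophrenia-spectrum component placed in the BP-I arm would push the estimated overlap upward. If this happened in one country only, it would also add between-country differences that come from the case definition rather than from ancestry.

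**Working it through.** **1. Which texts conflict**

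| Place in protocol | Case diagnosis |
|---|---|
| 2.2 Significance | BP-I only, for homogeneity |
| 5.5 Case inclusion | DSM-5 BP-I |
| 6.1 Korea | Bipolar I |
| 6.1 Singapore | As the study criteria |
| 6.1 Taiwan, case paragraph | BP-I or manic-type schizoaffective disorder |
| 6.1 Taiwan, criteria sentence | As the study criteria, plus exclusions that omit schizoaffective disorder |

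The two Taiwan statements cannot both hold. If 5.5 governs, schizoaffective patients are approached and later rejected at the SCID-5. If the Taiwan case paragraph governs, they pass as cases. No sentence gives precedence, a cap or a flag.

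**2. The plan's own totals (table in 5.4)**

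Cases: Japan 2,000 + India 10,000 + Korea 4,000 + Singapore 500 + Taiwan 3,000 = 19,500. Controls: 1,000 + 10,000 + 2,000 + 500 + 1,500 = 15,000. Both agree with the stated totals.

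**3. Taiwan's weight**

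- Of all recruited cases: 3,000 / 19,500 = 15.4%.
- Of East Asian cases (section 3.3 counts Taiwan, Japan, South Korea and Singapore): 3,000 / (2,000 + 4,000 + 500 + 3,000) = 3,000 / 9,500 = 31.6%.
- Section 8.3 instead has 2,400 Taiwan cases giving blood. On that count the East Asian share is 2,400 / 8,900 = 27.0%.

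**4. How many cases could be schizoaffective**

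Let f be the schizoaffective fraction of Taiwan cases. The protocol does not give it, so the values below are assumptions. Number = f × 3,000; shares = f × 3,000 / 9,500 and f × 3,000 / 19,500.

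| Assumed f | People | Of East Asian cases | Of all recruited cases |
|---|---|---|---|
| 0% (SCID-5 enforces 5.5) | 0 | 0% | 0% |
| 5% | 150 | 1.6% | 0.8% |
| 10% | 300 | 3.2% | 1.5% |
| 20% | 600 | 6.3% | 3.1% |

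**5. Illustrative effect on the BP-I/schizophrenia genetic correlation**

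Assumptions, none from the protocol: case effects mix linearly, heritabilities are equal, the true correlation is r, and a schizoaffective case is a proportion s schizophrenia-like (s = 0.5 to 1). With contaminated share m and w = m × s, the apparent correlation is

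r′ = [(1 − w)r + w] / √[(1 − w)² + w² + 2w(1 − w)r].

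For r = 0.6, m = 0.0316, s = 1: (0.9684 × 0.6 + 0.0316) / √(0.9378 + 0.0010 + 0.0367) = 0.6126 / 0.9877 = 0.620.

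Pooled East Asian results at r = 0.6, for s from 0.5 to 1:

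- f = 5%: 0.605 to 0.610
- f = 10%: 0.610 to 0.620
- f = 20%: 0.620 to 0.641

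At f = 20% and s = 1, r = 0.5 becomes 0.548 and r = 0.8 becomes 0.822. The shift is upward in every case and no more than about 0.05 over these values. Across all recruited Asian cases the contaminated share is about half as large, so the shift is smaller again.

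**The case against.** The best defence is that the safeguards may already work. Taiwan declares its criteria consistent with the study's, the SCID-5 is used to check that cases meet the inclusion criteria, and a second staff member confirms eligibility before enrolment. Read that way, no schizoaffective patient is ever counted. Item-level symptom data would also allow separation later, and the definition of the analysis set may stand in a statistical analysis plan that is not shown. This is a fair argument that the number could be zero. It does not remove the conflict, because the SCID-5 enforces whichever criterion it is given and Taiwan has been given two. The wider reading has some support: Taiwan excludes schizophrenia without mentioning schizoaffective disorder, and its target was set from caseloads for more than one diagnosis.

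Three stronger readings are tempting, and the documents do not support them.

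- A reader might infer that about a third of East Asian cases are contaminated. The 31.6% is Taiwan's whole contribution; it would be the contaminated share only if every Taiwan case were schizoaffective.
- A reader might infer a large distortion of the genetic correlation. That comes from looking at Taiwan alone and taking the true correlation as zero. In the formula above, w = 0.20 and r = 0 give 0.20 / √0.68 = 0.24. Section 9.1 itself plans to use pleiotropy across psychiatric disorders, and Aim 3c analyses a pooled Asian sample.
- A reader might infer that Taiwan's extra exclusions (intellectual disability, dementia, HIV) apply to cases only and so bias rare-variant comparisons. The Taiwan text also requires controls to be free of any psychiatric history, which plausibly covers dementia and may cover intellectual disability. It states no degree of intellectual disability, and nothing shows a consequence for HIV.

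**Conclusion.** The contradiction is established. Taiwan, planned to supply 15.4% of recruited cases and 31.6% of East Asian cases (27.0% on the blood-sample count), states a case diagnosis that section 5.5 does not admit, while claiming consistency with it.

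Contamination is possible but not shown. It depends on an unstated fraction: zero if section 5.5 is enforced at the SCID-5, and 150 to 600 people if that fraction is 5% to 20%. The direction of any bias, toward overstated BP-I/schizophrenia overlap, is reasonably clear. Its size cannot be fixed from the documents and is probably modest in the pooled sample, given the mixture assumptions stated above. The point rests on the case definition being ambiguous at a site about to enrol, not on a demonstrated large bias.

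**What to change.** Reconcile the Taiwan case text in 6.1 with the case criteria in 5.5 and the SCID-5 confirmation step in 5.6, in one of two ways:

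1. Remove schizoaffective disorder from the Taiwan case paragraph, so that Taiwan recruits BP-I only.
2. If Taiwan is to go on enrolling these patients, code them from the SCID-5 as a separate group. Leave them out of the 3,000 and 19,500 BP-I counts and out of the BP-I association analyses, and use them only in cross-disorder or sensitivity analyses.

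Either way, state that the SCID-5 check is made against the 5.5 criterion.

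The cost is a wording amendment through the local and Harvard IRBs. No new instrument is needed, since the mood and psychotic modules are already administered to cases. The downside is that Taiwan may take somewhat longer to reach 3,000 BP-I cases.
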